7.2. Method of Treatment Assignment

Patients who enter the PK lead-in period will be assigned a dose based on age. Pharmacokinetic samples will be collected as described in Section 9.5. Doses of subsequent patients who enter the PK lead-in period may be adjusted until a dose is found that produces exposures within the range produced by baricitinib 4-mg in adults with RA. All patients who enter the OLLI period will receive a fixed age-based dose of baricitinib as determined in the PK lead-in period.

Patients who meet the PedACR30 response criteria at the end of the OLLI period will be randomized in a 1:1 ratio (baricitinib age-based dose or matching placebo) to double-blind treatment at Week 12. The randomization will be stratified by history of prior bDMARD use (Yes versus No), the JIA category (polyarticular and extended oligoarticular versus ERA and

JPsA), and predose exposure ESR category (elevated [>20 mm/hour] and not elevated in the polyarticular JIA patients). Assignment to treatment groups will be determined by a computer-generated random sequence using an interactive web-response system (IWRS). The IWRS will be used to assign bottles containing double-blind investigational product to each patient. All patients <6 years of age will receive oral suspension. Patients ≥ 6 to <12 years old have the option of receiving the oral suspension. Patients >12 years will be supplied tablets only.

Site personnel will confirm that they have located the correct packages by entering a confirmation number found on the packages into the IVRS or IWRS before dispensing to the patient.

Refer to Section 5.1.2 for additional information regarding dosing in the Safety/PK assessment and OLLI period.

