All safety data will be descriptively summarized in each treatment period using corresponding populations. Comparison between baricitinib and placebo will be performed during the DBW period for the DBW population. The Fisher exact test will be used for the AEs, discontinuations, and other categorical safety data for between-treatment-group comparisons in the DBW period. Continuous vital signs, body weight, and other continuous safety variables, including laboratory variables, will be analyzed using ANCOVA with treatment and baseline value in the model in the DBW population.

Any change to the data analysis methods described in the protocol will require an amendment ONLY if it changes a principal feature of the protocol. Any other change to the data analysis

methods described in the protocol, and the justification for making the change, will be described in the clinical study report. Additional exploratory analyses of the data will be conducted as deemed appropriate. Complete details of the planned analyses will be documented in the SAP.

The SAP was approved before the first patient visit in Study JAHV.

Missing Data Imputation

The following methods for imputation of missing data will be used:

1. Nonresponder imputation (NRI): All patients who discontinue the study will be defined as nonresponders for the NRI analysis for categorical variables, such as PedACR30/50/70/90/100, from the time of discontinuation and onward.
2. Last observation carried forward (LOCF): The LOCF method will be used for the analysis of continuous endpoints (unless otherwise stated). For patients who discontinue the study, the last nonmissing observation will be carried forward to the subsequent time points for evaluation.

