10.3.3. Efficacy Analyses

10.3.3.1. Primary Analyses

The primary efficacy endpoint is time to disease flare (flare defined as worsening of $\geq 30\%$ in at least 3 of the 6 PedACR core criteria for JIA and an improvement of $\geq 30\%$ in no more than 1 of the criteria) during the DBW period for the DBW population. If either the number of joints with active arthritis or the number of joints with limitation of motion are used in the calculation of flare for a study visit, then a minimum worsening of at least 2 active joints or 2 joints with limitation of motion must be present. An active joint is defined as a joint with swelling or, in the absence of swelling, limitation of motion accompanied by pain on motion and/or tenderness. If either the Physician's Global Assessment of Disease Activity or the Parent's Global Assessment of Well-Being are used in the calculation of flare for a study visit, then a minimum worsening (as defined in the SAP) on the visual analogue scale (VAS) must be present. If ESR or CRP is used in the definition of "flare" and counts towards worsening, then the second value for ESR or CRP used in the calculation must be above the upper limit of normal for ESR (>20 mm/hour) or CRP. In JAHV, for primary analysis, disease flare definition will only use ESR.

The 6 PedACR core criteria (Gianni et al. 1997) includes:

- Number of active joints (defined as a joint that is swollen or in the absence of swelling has loss of passive motion accompanied by either pain on motion or joint tenderness) in 73 joints
- Number of joints with limited range of motion in 69 joints
- Physician's Global Assessment of Disease Activity
- Parent's Global Assessment of Well-Being
- Physical function as assessed by the CHAQ
- Acute-phase reactant (hsCRP and ESR)

Patients who discontinue the DBW period without experiencing a flare will have their data censored. A stratified logrank test across all JIA subtypes will be used as the primary analysis method. Survival curves will be estimated using the Kaplan–Meier method for all "time-to" variables in the DBW period.

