5.3. Method of Assignment to Treatment

Patients who enter the PK lead-in period will be assigned a dose based on age. Doses of subsequent patients who enter the PK lead-in period may be adjusted until a dose is found that produces exposures within the range produced by baricitinib 4-mg in adults with RA. All patients who enter the OLLI period will receive a fixed age-based dose of baricitinib as determined in the PK lead-in period.

Patients who meet the PedACR30 response criteria at the end of the OLLI period will be randomized in a 1:1 ratio (baricitinib age-based dose or matching placebo) to double-blind treatment at Week 12. The randomization will be stratified by:

- history of prior bDMARD use (Yes versus No)
- the JIA categories (polyarticular and extended oligoarticular [combined] versus ERA and JPsA [combined])
- Predose exposure erythrocyte sedimentation rate (ESR) categories (elevated [>20 mm/hour] and not elevated) in the polyarticular JIA patients

Assignment to treatment groups will be determined by a computer-generated random sequence using an interactive web-response system (IWRS). The IWRS will be used to assign bottles containing double-blind investigational product to each patient. All patients <6 years of age will receive oral suspension. Patients ≥ 6 to <12 years old have the option of receiving the oral suspension. Patients >12 years will be supplied tablets only. Site personnel will enter the confirmation number found on the bottles into the IWRS, which confirms that they have located the correct bottles.

6. A Priori Statistical Methods

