6.1.4. Analysis Methods

The primary endpoint will be the time-to-flare during the DBW period for randomized patients. Patients who discontinue or complete the DBW period without experiencing a flare will have their data censored at the time of their discontinuation date or completion date. The censored patients will contribute to the at-risk set in the stratified logrank test. Survival curves will be estimated using the Kaplan–Meier method in the DBW period. Treatment comparisons will be performed using a stratified log-rank test across JIA categories (polyarticular and extended oligoarticular [combined] versus ERA and JPsA [combined]) for the DBW population in the DBW period. Treatment comparisons may also be analyzed using a Cox proportional hazards model adjusted for stratification variables. The hazard ratio with 95% CIs will be reported. And the similarity of treatment effect across JIA categories (polyarticular and extended oligoarticular [combined] versus ERA and JPsA [combined]) will be evaluated using Cox proportional hazards regression adjusted for stratification variables. If any of these variables are redundant for a particular model, they will be dropped.

Secondary efficacy and health outcomes analyses ([Table JAHV.6.4](#) and [Table JAHV.6.5](#)) will be based on treatment period and respective study populations.

Efficacy, health outcomes, and safety data collected in OLLI period will be summarized without inferential statistics.

In the DBW period, the main analysis of categorical efficacy variables and health outcomes variables will use a logistic regression analysis with treatment, JIA categories (polyarticular and extended oligoarticular [combined] versus ERA and JPsA [combined]), predose exposure ESR categories (elevated [>20 mm/hour] and not elevated), history of prior bDMARD use (Yes or No) as covariates in the model. The p-value and 95% CI for the odds ratio from the logistic regression model are used for statistical inference.

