In the DBW period, the main analysis for all continuous efficacy and health outcomes variables will use analysis of covariance (ANCOVA) model with treatment, JIA patient categories (polyarticular and extended oligoarticular [combined] versus ERA and JPsA [combined]), predose exposure ESR categories (elevated [>20 mm/hour] and not elevated), history of prior bDMARD use (Yes or No), and baseline score as covariates in the model. For ESR and high-sensitivity C-reactive protein (hsCRP) analysis, predose ESR level categories will not be included as a covariate. Type III sums of squares for the least-squares mean (LSM) will be used for the statistical comparison of treatment groups, and the LSM difference, standard error, p-value and 95% CI will also be reported. The LOCF approach will be used to impute missing data.

The mixed model repeated measures (MMRM) analysis will also be considered as a supplemental analysis method. The MMRM will use a restricted maximum likelihood (REML) estimation. The model will include treatment, JIA patient categories (polyarticular and extended oligoarticular [combined] versus ERA and JPsA [combined]), predose exposure ESR categories (elevated [>20 mm/hour] and not elevated), history of prior bDMARD use (Yes or No), visit, treatment-by-visit-interaction, baseline score and baseline-by-visit-interaction as fixed effects. If any of these are redundant for a particular model, they will be dropped. An unstructured (co)variance structure will be used to model the between- and within-patient errors. If this analysis fails to converge, the heterogeneous autoregressive [ARH(1)], followed by the heterogeneous compound symmetry (CSH), followed by the heterogeneous Toeplitz (TOEPH) will be used. The Kenward-Roger method will be used to estimate the degrees of freedom. Type III tests for the LSM will be used for the statistical comparison. The LSM difference, standard error, p-value, and 95% CI will also be reported.

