6.10. Efficacy Analyses

6.10.1. Primary Outcome and Methodology

Time to disease flare (time is measured by week) is used as the primary outcome, which will be calculated as follows:

$$(\text{Date of Flare} - \text{Date of Randomization in the DBW} + 1)/7$$

The flare-ESR is calculated based on the flare definition and PedACR core criteria defined in Section 4.1, Table JAHV.4.1, Table JAHV.4.2, and Table JAHV.6.6, and uses ESR as acute-phase reactant. The detail of disease flare calculation is documented in separate disease flare and PedACR response calculation algorithm document. Patients completing the DBW period without flare will be censored at the date of completion (ie, the date of the last visit in the period).

Patients who discontinued treatment early in the DBW period without flare will be censored at the treatment discontinuation date.

The primary analysis of the study is to test for the hypotheses that baricitinib is superior to placebo in prolonging the time to disease flare in PedACR 30 responders from Week 12 to Week 44 using the DBW population.

A stratified logrank test will be used as the primary analysis method, in which the log-rank test will be stratified on the JIA categories:

- polyarticular and extended oligoarticular[combined]
- enthesitis-related JIA and JPsA[combined]

The p-value and median time to flare (if applicable) by treatment group will be reported. Treatment comparisons may also be analyzed using a Cox proportional hazards model adjusted for stratification variables. The hazard ratio with 95% CIs will be reported. The Kaplan-Meier product limit method will be used to estimate the survival curves for time-to flare. Time-to flare will also be summarized graphically by treatment group using Kaplan-Meier techniques.

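### The primary log-rank test is stratified on one of the three randomization factors; adding the other two is a cheap, optional efficiency gain, not the correction of an error

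*SAP*

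**What the plan says.** Protocol 7.2: "The randomization will be stratified by history of prior bDMARD use (Yes versus No), the JIA category", with predose ESR as a third factor. SAP 5.3 lists the same three and words the third as "Predose exposure erythrocyte sedimentation rate (ESR) categories (elevated [>20 mm/hour] and not elevated) in the polyarticular JIA patients".

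The primary test uses one of them. SAP 6.10.1: "A stratified logrank test will be used as the primary analysis method, in which the log-rank test will be stratified on the JIA categories". The two levels are polyarticular with extended oligoarticular, and ERA with JPsA. SAP 6.1.4 agrees: "Treatment comparisons will be performed using a stratified log-rank test across JIA categories". Protocol 10.3.3.1 is worded differently: "A stratified logrank test across all JIA subtypes will be used as the primary analysis method". Neither document says why prior bDMARD use and ESR are left out.

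SAP 6.2 makes adjustment for all three factors the default for statistical models but leaves room for exceptions. The main logistic, ANCOVA and MMRM models in SAP 6.1.4 carry all three. For ESR and hsCRP outcomes "predose ESR level categories will not be included as a covariate", and the mTSS model in SAP 6.11.1 uses none of the three.

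SAP 6.1.4 and 6.10.1 both list a Cox treatment comparison adjusted for the stratification variables, but only as optional. Both then state without condition that the hazard ratio and its 95% CI are reported. The firm Cox commitment has another purpose: similarity of the treatment effect across JIA categories "will be evaluated using Cox proportional hazards regression adjusted for stratification variables" (SAP 6.1.4, repeated in 6.16). The only other log-rank test, in SAP 6.11, is unstratified, optional and exploratory.

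**The concern.** Stratified randomization balances the arms on all three factors. A log-rank test that ignores two of them computes its variance as if the arms could still differ by chance on those two. If they predict flare, that variance is too large: the test rejects less often than 5% under the null and loses power under the alternative.

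The documents do not quantify whether either factor predicts flare. For ESR a link is plausible but unproven. ESR is one of the six flare components and counts towards worsening only above 20 mm/hour (SAP Table JAHV.6.4), which is also the stratification cut-off.

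The plan is also uneven. The secondary analysis of the proportion with flare uses the logistic model with all three factors, while the primary test of the same event uses one.

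**Working it through.** **1. The plan's own figure.** Inputs from SAP 5.2: 64 per arm, flare 35% against 60%, two-sided 5%, dropout at most 10%.

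- Exponential hazard ratio: ln(0.65)/ln(0.40) = 0.470.
- Expected flares: 64 × (0.60 + 0.35) = 60.8; with 10% dropout, 60.8 × 0.9 = 54.7.
- Schoenfeld power: Φ(√54.7/2 × |ln 0.470| − 1.96) = Φ(0.83) = 79.7%. Without dropout it is 83.7%.

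The stated power of about 80% is reproduced.

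**2. Comparing the two tests.** Simulation of 100,000 trials per setting, both tests run on the same trials (Monte Carlo SE of each power difference 0.05-0.08 points).

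- From the documents: 128 patients, 1:1, eight four-weekly visits over 32 weeks, 10% dropout, overall flare held at 60% and 35%.
- Assumed, not in the documents: permuted blocks of 4, exponential flare times, prior bDMARD use 50%, elevated ESR 40%, ERA/JPsA 20% or 8% (10/128 = 7.8%, the minimum in Protocol 5.2), extended oligoarticular 15% of its combined category.
- Six strata if the ESR split covers the whole combined polyarticular category: 2 × 3. Eight if extended oligoarticular patients are not split by ESR and form their own group: 2 × 4. The eight-strata reading fits the literal wording of SAP 5.3.
- Sparse strata are pooled by the example rule given under the fix.

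Power, by the assumed flare hazard ratio (HR) of both omitted factors. The first two columns are for six strata and ERA/JPsA 20%; gains are in percentage points, from unrounded values:

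| HR of both | JIA-only | All strata, pooled | Gain, six strata, 20% | Gain, six strata, 8% | Gain, eight strata |
|---|---|---|---|---|---|
| 1 | 80.9% | 80.5% | −0.5 | −0.4 | −0.7 |
| 1.5 | 81.4% | 81.8% | +0.4 | +0.8 | +0.1 |
| 2 | 82.8% | 85.1% | +2.3 | +2.9 | +1.5 |
| 3 | 85.0% | 90.5% | +5.4 | +6.4 | +4.1 |

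With only one factor prognostic, the change at HR 1.5 is +0.1 (bDMARD) or −0.1 (ESR), and at HR 2 it is +0.9 or +1.0. Eight strata without pooling cost 1.0 point when neither factor matters. JIA-only power stays above 80% because the overall flare rates are held fixed, so the treatment HR within strata strengthens: 0.47, 0.46, 0.44 and 0.40 down the rows.

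**3. Type I error**, both arms at 47.5% flare, HR 1, 1.5, 2, 3:

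- JIA-only: 5.0%, 4.7%, 4.1%, 3.0%.
- All strata, pooled: 5.1%, 5.0%, 4.9%, 4.7%.

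**4. Cross-check.** A separate simulation (20,000 trials per setting, six strata, no pooling) gave power for JIA-only against all strata of 80.6% vs 80.0%, 80.9% vs 81.6%, 82.5% vs 85.1% and 85.2% vs 91.2% at HR 1, 1.5, 2 and 3. The pattern is the same.

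**The case against.** The plan is entitled to this choice, and even the sign of the benefit is unknown. The documents give no prognostic effect for either factor. The change loses a little at HR 1, is about neutral at HR 1.5, and gains more than about 1 point only if both factors have HR near 2 or above. HR 3 for both implies a nine-fold spread in hazard (3 × 3), which nothing in the documents supports. SAP 6.11 already worries about small numbers in two JIA categories, and more strata go the other way: in the simulations the ERA/JPsA bDMARD strata had to be merged in 53-69% of trials at 20% ERA/JPsA and over 99% at 8%. All of this stands, and it is why the change is optional. Pooling meets the sparse-data point, since most of the gain comes from the polyarticular strata.

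Four stronger readings are tempting, and the documents do not support them:

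- *The SAP contradicts itself.* It does not: SAP 6.2 allows exceptions, and 6.1.4 and 6.10.1 specify one.
- *The test is invalid.* Omitting a balanced factor makes it conservative, not anti-conservative.
- *The trial is underpowered.* If 0.470 were the hazard ratio within strata, JIA-only power would fall to 76.5-77.6% with both factors at HR 2 and 69.5-71.2% at HR 3. But SAP 5.2 states overall flare percentages, so 0.470 is a marginal value.
- *No all-factor treatment comparison is planned.* One is, by Cox model, in both SAP 6.1.4 and 6.10.1, but only as optional.

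**Conclusion.** The primary log-rank uses one of three randomization factors without explanation. The test is valid, meets its stated power, and puts no conclusion at risk. Stratifying by the groups already used for randomization would gain about 1.5-3 percentage points of power if both omitted factors have HR 2, about 4-6 at HR 3, almost nothing at HR 1.5, and would cost about 0.4-1 point if neither matters. The ranges cover six or eight strata and rest on assumed prevalences and prognostic strengths. This is an optional efficiency gain.

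Two wording gaps need closing whatever is decided on strata. The promised hazard ratio comes from a model that need not be run. And the protocol's subtypes are not plainly the SAP's two combined categories.

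**What to change.** Before unblinding:

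- Stratify the primary log-rank by the strata actually used in the interactive web-response system, and state whether the ESR strata include extended oligoarticular patients.
- Prespecify a pooling rule that uses no treatment codes. For example: merge the two bDMARD strata within a JIA/ESR group if either has fewer than 5 flares over both arms; if the merged stratum is still below 5, join it to the ESR group with the most flares in the same JIA category; never go coarser than the SAP's two JIA categories. The threshold of 5 is illustrative.
- Keep the JIA-only log-rank as a sensitivity analysis.
- Make the Cox model adjusted for the stratification variables mandatory in SAP 6.1.4 and 6.10.1, as the source of the hazard ratio and 95% CI.
- Reconcile Protocol 10.3.3.1 with the SAP's categories.

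If JIA-only stratification stays primary, add the all-strata log-rank as a prespecified sensitivity analysis. That needs SAP text only, but it does not recover power in the primary analysis.

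Cost: no new data; up to about 1 point of power if neither factor is prognostic; thin ERA/JPsA strata to manage; and possibly a protocol amendment. Under Protocol 10.3.1 a change of method "will require an amendment ONLY if it changes a principal feature of the protocol", and the sponsor must decide whether this one does.

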6.10.2. Secondary Efficacy Analyses

Secondary efficacy and health outcomes analyses ([Table JAHV.6.4](#)) will be based on treatment periods with the respective population at each visit. The analysis method is described in [Table JAHV.6.5](#). There will be no adjustment for multiple comparisons.

Table JAHV.6.4. Description and Derivation of Primary, Secondary Efficacy Endpoints and Health Outcomes

Measure	Description	Variable	Derivation/Comment	Imputation Approach if with Missing Components
Disease flare	
Disease flare is defined as a worsening of $\geq 30\%$ in at least 3 of the 6 PedACR core criteria for JIA and an improvement of $\geq 30\%$ in no more than 1 of the criteria from the patient's condition at randomization baseline. In disease flare-ESR, ESR measure is used as acute-phase reactant in the core criteria.
 
 • If either the number of joints with active arthritis or the number of joints with limitation of motion are used in the calculation of flare for a study visit, then a minimum worsening of at least 2 active joints or 2 joints with limitation of motion must be present. • An active joint is defined as a joint with swelling or, in the absence of swelling, limitation of motion accompanied by pain on motion and/or tenderness. • If either the Physician's Global Assessment of Disease Activity or the Parent's Global Assessment of Well-Being are used in the calculation of flare for a study visit, then a minimum worsening of at least 20 mm in 0-100 mm visual analogue scale (VAS) must be present. • If ESR is used in the definition of "flare" and counts towards worsening, then the second value for ESR used in the calculation must be above the upper limit of normal for ESR (>20 mm/hour). 	Time to disease flare	
The details of disease flare calculation are documented in separate disease flare and PedACR response calculation algorithm document.
 
Calculation: Date of disease flare-ESR minus date of randomization+1
	
Component is missing if baseline or postbaseline value is missing. LOCF will be applied for post baseline missing values. If more than 3 components are missing, there will not be sufficient information; thus, the patient will be considered as a non-flare patient.

		Proportion of patients with disease flare	The detail of disease flare calculation is documented in separate disease flare and PedACR response calculation algorithm document.	
The details of handling of missing data are documented in separate disease flare and PedACR response calculation algorithm document.

Secondary Efficacy Endpoint Analyses

Measure	Description	Variable	Derivation/Comment	Imputation Approach if with Missing Components
PedACR response	
Pediatric American College of Rheumatology (PedACR x%) responder is defined as patients who demonstrate disease response improvement of $\geq x\%$ in at least 3 of 6 Pediatric American College of Rheumatology (PedACR) core response variables and $>30\%$ worsening in not more than 1 of the remaining variables. (PedACR30; Giannini et al. 1997). When PedACR response is analyzed as secondary endpoint, ESR measure is used as acute-phase reactant in the core criteria.
	
PedACR 30/50/70/90/100 response rates (compare to patient's condition prior to first dose of investigational product)
	
The detail of disease flare calculation is documented in separate disease flare and PedACR response calculation algorithm document.
	
Component is missing if baseline or postbaseline value is missing. LOCF will be applied for post baseline missing values. If more than 3 components are missing, there will not be sufficient information; thus, the patient will be considered as a non-responder.
 
The detail of handling of missing data is documented in separate disease flare and PedACR response calculation algorithm document.

Secondary Efficacy Endpoint Analyses

Measure	Description	Variable	Derivation/Comment	Imputation Approach if with Missing Components
Active joint count	Number of active joints (defined as a joint that is swollen or in the absence of swelling has loss of passive motion accompanied by either pain on motion or joint tenderness) in 73 joints.	Change from baseline of active joint count	Calculation: Change from baseline: observed active joint count at visit minus baseline active joint count	Missing if baseline or postbaseline value is missing. LOCF will be applied for post baseline missing values.
Limited range of motion joint count	Number of joints with limited range of motion in 69 joints	Change from baseline of limited of motion joint count	Calculation: Change from baseline: observed limited range of motion joint count at visit minus baseline limited range of motion joint count	Missing if baseline or postbaseline value is missing. LOCF will be applied for post baseline missing values.
Physician's global assessment of disease activity (VAS)	The Physician's Global Assessment of Disease Activity is used to assess the patient's current disease activity, as it relates to their signs and symptoms. The instrument uses a 21 circle VAS ranging from 0 to 10 (using 0.5 increments) where 0 = "no activity" and 10 = "maximum activity" (Filocamo et al. 2010).	Change from baseline of physician's global assessment of disease activity	Calculation: Change from baseline: observed score at visit minus baseline score	Missing if baseline or postbaseline value is missing. LOCF will be applied for post baseline missing values.
Parent's global assessment of overall well-being measured by CHAQ (10cm VAS)	The parent is generally asked to make a global assessment of the child's overall well-being on a 10 cm VAS, with anchors of '0 = very good' and '10 = very poor', which is located at the bottom of the Childhood Health Assessment Questionnaire (CHAQ) questionnaire	Change from baseline of parent's global assessment of overall well-being	Calculation: Change from baseline: observed score at visit minus baseline score	Missing if baseline or postbaseline value is missing. LOCF will be applied for post baseline missing values.

Secondary Efficacy Endpoint Analyses

Measure	Description	Variable	Derivation/Comment	Imputation Approach if with Missing Components
Physical function as measured by CHAQ (0-3)	
The Childhood Health Assessment Questionnaire (CHAQ) assesses health status and physical function over the past week in children with juvenile arthritis over the past week, which the parent or legal guardian completes, regardless of the age of the patient.
 
Physical function is measured by CHAQ from disability index. The Disability Index contains 30 items grouped into the following 8 domains (not including assistive devices/aids questions): physical function, dressing, and grooming (4 items), arising (2 items), eating (3 items), walking (2 items), hygiene (5 items), reach (4 items), grip (5 items), and activities (5 items). Each item is scored from 0 to 3 (0 = no difficulty; 1 = some difficulty; 2 = much difficulty; 3 = unable to do or not applicable) (Singh et al. 1994). The total score is the average of domain score, which is range from 0 to 3.
 
At least 6 domains are required in calculation.
	Change from baseline of physical function	
The details of physical function calculations are documented in separate CHAQ instruction document.
 
Calculation: Change from baseline: observed score at visit minus baseline score
	Missing if baseline or postbaseline value is missing. LOCF will be applied for post baseline missing values.
hsCRP (mg/L)	The hsCRP test is a highly sensitive quantification of C-Reactive protein (CRP), an acute-phase protein that increases during inflammation.	Change from baseline of hsCRP	Calculation: Change from baseline: observed lab value at visit minus baseline lab value	Missing if baseline or postbaseline value is missing. LOCF will be applied for post baseline missing values.

Secondary Efficacy Endpoint Analyses

Measure	Description	Variable	Derivation/Comment	Imputation Approach if with Missing Components
ESR (mm/hr)	An erythrocyte sedimentation rate (ESR) is a type of blood test that measures how quickly erythrocytes (red blood cells) settle at the bottom of a test tube that contains a blood sample. Normally, red blood cells settle relatively slowly. A faster-than-normal rate may indicate inflammation in the body.	Change from baseline of ESR	Calculation: Change from baseline: observed lab value at visit minus baseline lab value	Missing if baseline or postbaseline value is missing. LOCF will be applied for post baseline missing values.
Physical Summary Score (PhS) and Psychosocial Summary Score (PsS)	Physical Summary Score (PhS) and Psychosocial Summary Score (PsS) from Child Health Questionnaire-Parent Form 50 (CHQ-PF50) will be used to address physical and psychosocial health status. The CHQ-PF50 is a generic QOL instrument designed to capture the physical, emotional, and social components of health status of children as well as caregiver burden over the past 4 weeks (HealthActCHQ 2013). The CHQ-PF50 is completed by the parent and has been validated for use in JIA patients (Ruperto et al. 2001).	Change from baseline in the Physical Summary Score (PhS) and Psychosocial Summary Score (PsS) of the Child Health Questionnaire-Parent Form 50 (CHQ-PF50)	The Physical Summary Score (PhS) and Psychosocial Summary Score (PsS) will be scored according to the manual, "CHQ Scoring and Interpretation manual". (HealthActCHQ 2013). Calculation: Change from baseline: observed score at visit minus baseline score	Missing if baseline or postbaseline value is missing. LOCF will be applied for post baseline missing values.
Caregiver burden	Caregiver burden is measured by Parental Impact-Time and Parental Impact-Emotion scales from CHQ-PF50 will be used to address burden to the parent/legal guardian.	Change from baseline of caregiver burden score measured by the Parental Impact-Time and Parental Impact-Emotion scales of the CHQ-PF50	The caregiver burden will be scored according to the manual, "CHQ Scoring and Interpretation manual". (HealthActCHQ 2013). Calculation: Change from baseline: observed score at visit minus baseline score	Missing if baseline or postbaseline value is missing. LOCF will be applied for post baseline missing values.

Secondary Efficacy Endpoint Analyses

Measure	Description	Variable	Derivation/Comment	Imputation Approach if with Missing Components

Inactive disease
	
Inactive disease is indicated by the presence of all of the following (Wallace et al. 2011):
 
 No joints with active arthritis based on JADAS-27 No fever, rash, serositis, splenomegaly, hepatomegaly, or generalized lymphadenopathy attributable to JIA as assessed by the investigator No active uveitis as assessed by the investigator Normal erythrocyte (ESR) or hsCRP (ie, within normal limits in the local laboratory or, if elevated, not attributable to JIA) Physician's Global Assessment of Disease Activity indicating no active disease (best possible score on scale [0]) Duration of morning stiffness less than 15 minutes In inactive disease analysis as secondary endpoint, ESR measure is used as acute-phase reactant measure. 	
Proportion of patients who achieved inactive disease
	
 Step 1: If joint with active arthritis isn't 0, stop; else Step 2: If there is fever, rash, serositis, splenomegaly, hepatomegaly, or generalized lymphadenopathy attributable, stop; else Step 3: If uveitis, stop; else Step 4: If ESR>20, stop; else Step 5: If physician's global assessment of disease activity isn't 0, stop; else Step 6: If stiffness >15min, stop; else Step 7: Conclude the patient achieved inactive disease status. 	
Missing if any component is missing. NRI will be applied to missing data.

Secondary Efficacy Endpoint Analyses

Measure	Description	Variable	Derivation/Comment	Imputation Approach if with Missing Components
Minimal disease activity	Minimal disease activity is calculated based on the scores from the Physician's Global Assessment of Disease Activity, Parent's Global Assessment of Patient's overall Well-Being, and the number of swollen joints as described in Consolaro et al. 2012.	Proportion of patients who achieved minimal disease activity	
 • if physician's global assessment of disease activity ≤ 3.5, and • if parent's global rating of patient's overall well-being ≤ 2.5, and • if swollen joint count ≤ 1, then conclude the patient reaches minimal disease activity; all else conclude the minimal disease activity is not reached. 	
Component is missing if baseline or postbaseline value is missing. LOCF will be applied for post baseline missing values.
 
If all components are missing after LOCF, NRI will be applied to missing data.

Secondary Efficacy Endpoint Analyses

Measure	Description	Variable	Derivation/Comment	Imputation Approach if with Missing Components
Disease remission	Remission is defined as inactive disease for at least 24 consecutive weeks (Wallace et al. 2011). In inactive disease as secondary endpoint, ESR measure is used as acute-phase reactant in the core criteria. Thus, the disease remission as secondary endpoint is based on ESR.	Proportion of patients who achieved minimal disease activity	
 At Visit 13, check if there are inactive disease status in all Visit 7, Visit 8, Visit 9, Visit 10, Visit 11, Visit 12, if yes, conclude the patient has achieved disease remission status. At Visit 14, check if there are inactive disease status at Visit 8, Visit 9, Visit 10, Visit 11, Visit 12, Visit 13, if yes, conclude the patient has achieved disease remission status. At Visit 15, check if there are inactive disease status at Visit 9, Visit 10, Visit 11, Visit 12, Visit 13, Visit 14, if yes, conclude the patient has achieved disease remission status. At Visit 16, check if there are inactive disease status at Visit 10, Visit 11, Visit 12, Visit 13, Visit 14, Visit 15, if yes, conclude the patient has achieved disease remission status. At Visit 17, check if there are inactive disease status at Visit 11, Visit 12, Visit 13, Visit 14, Visit 15, Visit 16, if yes, conclude the patient has achieved disease remission status. 	Missing if item is missing. NRI will be applied to missing data.

Secondary Efficacy Endpoint Analyses

Measure	Description	Variable	Derivation/Comment	Imputation Approach if with Missing Components
JADAS-27	
The JADAS-27 score is a validated composite disease activity measure for JIA (Consolaro et al. 2012). Recently, the scoring system was adapted to use the 27-joint count (Bazso et al. 2009) and hsCRP or ESR for the inflammatory marker component (Nordal et al. 2012). The JADAS 27 includes the following joints: cervical spine, elbows, wrists, metacarpophalangeal joints (from first to third), proximal interphalangeal joints, hips, knees, and ankles. In JADAS-27 analysis as secondary endpoint, ESR measure is used as acute-phase reactant measure,
	
Change from baseline of JADAS-27 score
	
JADAS-27 score (0-57) will be determined based on 4 components:
 
 • PHY: Physician’s Global Assessment of Disease Activity (0-10 VAS) • PGA: Parent’s Global Assessment of Patient’s overall Well-Being (0-100 mm VAS) • Joint27: Number of joints with active disease (27-joint assessment) • ESR (mm/hr) 
Calculation:
 
NormESR: Normalized ESR (0-10) NormESR=(ESR-20)/10
 
Scaled PGA= scaled Parent’s Global Assessment of Patient’s overall Well-Being (0-10) Scaled PGA=PGA/10
 
JADAS(ESR)27=PHY+ScaledPGA+Joint27+NormESR
 
Change from baseline: observed JADAS(ESR)-27 at visit minus baseline JADAS-27
	
Missing if baseline is missing: For observed value, missing if all the components are missing. LOCF will be applied for post baseline missing value. If at least one component is non-missing, LOCF will be applied on the missing components prior to LOCF being applied to the composite score

Secondary Efficacy Endpoint Analyses

Measure	Description	Variable	Derivation/Comment	Imputation Approach if with Missing Components
Pain (VAS)	The pain assessment item will be collected from the CHAQ.	Change from baseline of pain vas score	Calculation: Change from baseline: observed score at visit– baseline score	Missing if baseline or postbaseline value is missing. LOCF will be applied for post baseline missing value.

Abbreviations: CHQ-PF50 = Child Health Questionnaire-Parent Form 50; ESR = erythrocyte sedimentation rate; hsCRP = high-sensitivity C-reactive protein; JADAS = Juvenile Arthritis Disease Activity Score; JIA = juvenile idiopathic arthritis; LOCF = last observation carried forward; NRI = nonresponder imputation; PedACR = Pediatric American College of Rheumatology; VAS = Visual Analog Scale.

Table JAHV.6.5. Description of Analysis Period and Analysis Method of Secondary Endpoint and Health Outcome

